For each arm, the efficacy and toxicity will be monitored simultaneously using the Bayesian optimal phase 2 (BOP2) design (Zhou, Lee and Yuan, 2017). Specifically, let n denote the interim sample size and N denote the maximum sample size. Let Y_{eff} and Y_{tox} denote the binary efficacy and toxicity endpoints, with $Y_{eff} = 1$ and $Y_{tox} = 1$ indicating that patients experience efficacy and toxicity, respectively. We assume that the joint distribution of (Y_{eff}, Y_{tox}) follows a multinomial distribution with four elementary outcomes: $(Y_{eff}, Y_{tox}) = (1, 1), (1, 0), (0, 1)$ and $(0, 0)$. Let $\mathbf{p} = (P_{11}, P_{10}, P_{01}, P_{00})$ denote the probabilities of observing the four outcomes, and let $p_{eff} = Pr(Y_{eff} = 1)$, $p_{tox} = Pr(Y_{tox} = 1)$ and $p_{efftox} = Pr(Y_{eff} = 1, Y_{tox} = 1)$.

AML Arm:

The treatment is deemed unacceptable if $p_{eff} \leq 0.2$ or $p_{tox} > 0.2$. Thus, we will stop enrolling patients and claim that the treatment is unacceptable if

$$Pr(p_{eff} > 0.2 | data) < \lambda \left(\frac{n}{N} \right)^\alpha,$$

or

$$Pr(p_{tox} \leq 0.2 | data) < \lambda \left(\frac{n}{N} \right)^{\alpha/3},$$

where $\lambda=0.5$ and $\alpha=0.51$ are design parameters optimized to maximize the study power, i.e., probability of correctly concluding an efficacious and safe treatment as acceptable when $p_{eff} = 0.4$, $p_{tox} = 0.1$ and $p_{efftox} = 0.04$, while controlling that the probability of incorrectly claiming an ineffectual and toxic treatment, i.e., type I error, with $p_{eff} = 0.2$, $p_{tox} = 0.2$ and $p_{efftox} = 0.04$, to 10.4%. Note that in the safety stopping rule, the original publication of the design used the probability cutoff $\lambda(n/N)^\alpha$, here the attenuation factor 3 is added (i.e., $\alpha/3$) to obtain stricter interim stopping boundaries to enhance safety.

This optimization is performed assuming a vague Dirichlet prior $Dir(0.04, 0.16, 0.16, 0.64)$ for \mathbf{p} . The prior is chosen such that it corresponds to a prior effective sample size of 1 patient, and the prior estimates of p_{eff} and p_{tox} match the values specified when the treatment is unacceptable. The above decision rule leads to the following optimal stopping boundaries, in cohort size of 6.

Table 4: Optimized stopping boundaries for AML Arm

# patients treated	Stop if # response <=	OR # toxicity >=
6	0	2
12	1	3
18	3	4
24	4	6
30	6	7

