When the total number of AML patients reaches the maximum sample size of 30, we conclude that the treatment is acceptable if the number of responses are greater than 6, and the number of toxicities are less than 7; otherwise we conclude that the treatment is unacceptable. The go/no-go criteria in Table 4 are non-binding.

Below are the operating characteristics of the design based on 10000 simulations using the BOP2 web application (BOP2 V1.4.7.0), which is available at <http://www.trialdesign.org>.

Table 5: Operating characteristics for the interim futility and toxicity monitoring in AML Arm

Scenario	Pr(Eff)	Pr(Tox)	Pr(Eff & Tox)	Early Stopping (%)	Claim Acceptable (%)	Average Sample Size
1	0.20	0.20	0.040	85.03	10.44	12.8
2	0.40	0.10	0.040	25.31	73.93	24.8
3	0.40	0.25	0.120	80.66	15.88	13.4
4	0.15	0.30	0.045	98.07	0.77	8.5

MDS Arm:

The treatment is deemed unacceptable if $p_{eff} \leq 0.15$ or $p_{tox} > 0.2$. Thus, we will stop enrolling patients and claim that the treatment is unacceptable if

$$Pr(p_{eff} > 0.15 | data) < \lambda \left(\frac{n}{N} \right)^\alpha,$$

or

$$Pr(p_{tox} \leq 0.2 | data) < \lambda \left(\frac{n}{N} \right)^{\alpha/3},$$

where $\lambda=0.52$ and $\alpha=0.15$ are design parameters optimized to maximize the study power, i.e., probability of correctly concluding an efficacious and safe treatment as acceptable when $p_{eff} = 0.3$, $p_{tox} = 0.1$ and $p_{efftox} = 0.03$, while controlling that the probability of incorrectly claiming an ineffectual and toxic treatment, i.e., type I error, with $p_{eff} = 0.15$, $p_{tox} = 0.2$ and $p_{efftox} = 0.03$, to 9.8%. Note that in the safety stopping rule, the original publication of the design used the probability cutoff $\lambda(n/N)^\alpha$, here the attenuation factor 3 is added (i.e., $\alpha/3$) to obtain stricter interim stopping boundaries to enhance safety.

This optimization is performed assuming a vague Dirichlet prior $Dir(0.03, 0.12, 0.17, 0.68)$ for \mathbf{p} . The prior is chosen such that it corresponds to a prior effective sample size of 1 patient, and the prior estimates of p_{eff} and p_{tox} match the values specified when the treatment is unacceptable. The above decision rule leads to the following optimal stopping boundaries, in cohort size of 6.

Table 6: Optimized stopping boundaries for MDS Arm

# patients treated	Stop if # response \leq	OR # toxicity
		\geq
6	0	2
12	1	3
18	2	4
24	3	5
30	4	7

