When the total number of MDS patients reaches the maximum sample size of 30, we conclude that the treatment is acceptable if the number of responses are greater than 4, and the number

of toxicities are less than 7; otherwise we conclude that the treatment is unacceptable. The go/no-go criteria in Table 6 are non-binding.

Below are the operating characteristics of the design based on 10000 simulations using the BOP2 web application (BOP2 V1.4.7.0), which is available at <http://www.trialdesign.org>.

Table 7: Operating characteristics for the interim futility and toxicity monitoring in MDS Arm

Scenario	Pr(Eff)	Pr(Tox)	Pr(Eff & Tox)	Early Stopping (%)	Claim Acceptable (%)	Average Sample Size
1	0.15	0.20	0.030	88.41	9.77	11.5
2	0.30	0.10	0.030	34.21	65.36	23.0
3	0.30	0.25	0.075	86.01	12.85	12.5
4	0.10	0.30	0.030	98.89	0.69	7.8

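### The stated type I error (10.4% AML, 9.8% MDS) holds only if every interim stop is obeyed, yet the plan calls those stops non-binding

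*Combined protocol and SAP*

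**What the plan says.** All of this is in section 8.0, Phase II, in parallel text for the AML and MDS arms.

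- **The rule.** When a posterior probability falls below its cutoff, "we will stop enrolling patients and claim that the treatment is unacceptable if" the efficacy or the toxicity condition is met. No exception is given there.
- **The error claim.** λ and α maximise power "while controlling that the probability of incorrectly claiming an ineffectual and toxic treatment, i.e., type I error", to 10.4% at response 0.20 and toxicity 0.20 (AML), and to 9.8% at response 0.15 and toxicity 0.20 (MDS).
- **The safety cutoff.** The exponent is α/3 for toxicity, "to obtain stricter interim stopping boundaries to enhance safety".
- **The status of the rule.** Directly after the n = 30 decision rule, the AML text reads "otherwise we conclude that the treatment is unacceptable. The go/no-go criteria in Table 4 are non-binding" and the MDS text reads "otherwise we conclude that the treatment is unacceptable. The go/no-go criteria in Table 6 are non-binding". (Table 4 here is the AML stopping table; the phase 1b dose table carries the same number.)
- **The definition of unacceptable.** A treatment is unacceptable if response is at or below the null limit (0.20 AML, 0.15 MDS) or if toxicity exceeds 0.20. Either is enough.
- **The operating characteristics.** Table 5 ("Operating characteristics for the interim futility and toxicity monitoring in AML Arm") and its MDS counterpart, Table 7, give one set of figures each. Neither says that they assume every stop is followed.

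**The concern.** In this design most of the error control comes from early stopping. At the null point the plan's own tables show 85.03% (AML) and 88.41% (MDS) of trials stopping before 30 patients. A rate that depends so heavily on stopping cannot also be the rate of a design whose stops may be overridden. Overrides are legitimate, but then the stated error should not rely on the stops, or should say that it does.

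Two further ambiguities follow. The non-binding sentence covers the toxicity boundaries, which the plan tightened on purpose. It also comes straight after the n = 30 rule, and Tables 4 (AML) and 6 contain an n = 30 row, so a reader cannot tell whether the final rule binds.

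At stake is how a final claim of acceptable would be read. It would be judged against a false-positive rate of about 10%, with power and scenario 3 figures that rest on the same assumption.

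**Working it through.** **Inputs (section 8.0).** Looks at n = 6, 12, 18, 24, 30.
- AML: stop if responses ≤ 0/1/3/4/6 or toxicities ≥ 2/3/4/6/7. Acceptable at 30 if responses ≥ 7 and toxicities ≤ 6.
- MDS: stop if responses ≤ 0/1/2/3/4 or toxicities ≥ 2/3/4/5/7. Acceptable at 30 if responses ≥ 5 and toxicities ≤ 6.
- Null points (response, toxicity, both): (0.20, 0.20, 0.04) AML; (0.15, 0.20, 0.03) MDS.

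**Step 1: boundaries.** The stated Dirichlet priors have Beta marginals: Beta(0.2, 0.8) for AML response, Beta(0.15, 0.85) for MDS response and Beta(0.2, 0.8) for toxicity. With cutoffs λ(n/30)^α for response and λ(n/30)^(α/3) for toxicity (λ/α = 0.5/0.51 AML, 0.52/0.15 MDS), all ten rows of the two tables are reproduced.

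**Step 2: the plan's own figures.** I carried the joint count of responses and toxicities forward exactly in cohorts of 6, removing the paths that cross a boundary.

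| Claim acceptable, all stops obeyed | AML exact | AML printed | MDS exact | MDS printed |
|---|---|---|---|---|
| Scenario 1 (null) | 10.25% | 10.44% | 9.25% | 9.77% |
| Scenario 2 (power) | 74.05% | 73.93% | 64.96% | 65.36% |
| Scenario 3 | 15.87% | 15.88% | 12.50% | 12.85% |
| Scenario 4 | 0.78% | 0.77% | 0.57% | 0.69% |

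The standard error from 10000 simulations is about 0.3 points at 10%, so the scenario 1 gaps are 0.6 (AML) and 1.8 (MDS) standard errors. The printed figures are those of a fully obeyed design.

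**Step 3: no interim stop followed, n = 30 rule kept.** At the null points the joint probability equals the product of the marginals, so the error is a product of two binomial probabilities with n = 30.
- AML: Pr(responses ≥ 7 | 0.20) × Pr(toxicities ≤ 6 | 0.20) = 0.3930 × 0.6070 = 23.86%.
- MDS: Pr(responses ≥ 5 | 0.15) × Pr(toxicities ≤ 6 | 0.20) = 0.4755 × 0.6070 = 28.86%.

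**Step 4: partial overriding at the null point.**

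| Interim stops not followed | AML | MDS |
|---|---|---|
| None (all obeyed) | 10.25% | 9.25% |
| One whole look, at n = 6 / 12 / 18 / 24 | 12.2 / 11.1 / 12.4 / 10.5% | 11.5 / 10.4 / 10.2 / 10.7% |
| All futility stops | 13.8% | 15.2% |
| All toxicity stops | 17.7% | 17.6% |
| All | 23.9% | 28.9% |

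**Step 5: the other printed rows with no interim stop followed.** Power becomes 95.7% (AML) and 94.5% (MDS). Scenario 3 (active but too toxic) becomes 34.1% and 33.8%. Since scenario 3 also meets the plan's definition of unacceptable, 23.9% and 28.9% are not upper bounds on a wrong claim.

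**Step 6: supporting point.** Tables 5 and 7 have no row with response at the null limit and acceptable toxicity. Take toxicity 0.10, the value the plan uses for a safe treatment, and assume independence.
- Stops obeyed: 23.5% (AML) and 23.0% (MDS); over all feasible joint probabilities, 17.0–25.1% and 14.3–24.5%.
- No interim stop followed: 38.3% and 46.3% (ranges 36.7–38.7% and 45.0–46.7%).
- This is a boundary case. At response 0.15 (AML) or 0.10 (MDS), the obeyed-stops rate falls to 8.6% and 7.5%, below the stated error; with no interim stop followed it is 14.9% and 17.1%.

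**The case against.** The best defence is that 23.9% and 28.9% are an extreme. They require all four interim looks to be ignored, for futility and toxicity alike, with 30 patients always enrolled. Permission to override does not mean that no stop is ever followed, and ignoring a single look raises the exact error by at most 2.1 points in AML (10.25 to 12.38) and 2.3 in MDS (9.25 to 11.51). That is fair, and the figures should be presented as that case. But each single-look omission still raises the error, and the plan sets no limit on how many stops may be overridden.

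Second, the early-stopping and average-sample-size columns let a careful reader infer that the tables assume stopping, and the error statement is correct as a calibration at a disclosed point. Also true; but the text presents the rate as controlled, and the qualification is never written down.

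Third, the efficacy aim is preliminary. Section 8.5 plans a 95% credible interval, which would show a bare pass as uncertain (10.4–39.3% for 7/30 in AML, 5.9–31.3% for 5/30 in MDS), and asks for summaries to the IND Office for review and approval after every 10 patients per arm in phase 2. These limit the harm. Neither restores the stated rate, and the reviews do not fall at the looks of 6.

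Finally, the missing table row is a boundary case that depends on an assumed joint probability. That stands: it is supporting material, and the main point does not need it.

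**Conclusion.** The concern holds and should be fixed. The stated 10.4% and 9.8% are right for a design in which every interim stop is obeyed, and the plan as written is not that design. With the n = 30 rule kept, the error at the plan's own null point runs from 10.25% to 23.9% in AML and from 9.25% to 28.9% in MDS, depending on how many stops are followed. If the n = 30 rule is itself non-binding, no error rate can be stated.

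The result rests on the printed boundaries, cohorts of 6 and the plan's stated null probabilities; only the supporting point needs an added independence assumption. Confidence is high. The fault is in the error statement and the conflicting wording, not in the boundaries or the simulations.

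**What to change.** Reconcile the firm stopping sentence with the non-binding sentence in each arm, in one of two ways.

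1. **Remove the non-binding sentences.** Then 10.4% and 9.8% hold at the joint null.
2. **Keep them, and:**
   - restate 10.4%, 9.8% and the other rows of Tables 5 and 7 as figures with all stops obeyed;
   - state whether the n = 30 rule is applied;
   - with that rule applied, report the error with interim stops not followed at the joint null (23.9% AML, 28.9% MDS) and, as supporting information, at null-limit response with toxicity 0.10 (38.3%, 46.3%), calling neither an upper bound.

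As an optional addition under either choice, add one row per table, stating that independence is assumed:
- Table 5: (0.20, 0.10, 0.020), early stopping 68.5%, claim acceptable 23.5%, average sample size 17.1.
- Table 7: (0.15, 0.10, 0.015), early stopping 73.7%, claim acceptable 23.0%, average sample size 15.1.

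The cost is one reconciled sentence per arm. If the stops stay non-binding, add one restated figure and two added error figures per arm. The optional rows need one re-run of the same application. No extra patients are needed, and the boundaries and final rule stay as they are.

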After Phase 1b part of the trial is completed, select the MTD for each arm based on isotonic regression as specified in Liu and Yuan (2015). This computation is implemented by the shiny app "BOIN" available at <http://www.trialdesign.org>. Specifically for each arm, select as the MTD the dose for which the isotonic estimate of the toxicity rate is closest to the target toxicity rate. If there are ties, select the higher dose level when the isotonic estimate is lower than the target toxicity rate and select the lower dose level when the isotonic estimate is greater than or equal to the target toxicity rate. Furthermore, the RP2D will be selected based on safety and efficacy, in Arms A and B independently.

Operation Characteristics

Table 3 shows the operating characteristics of the Boin design based on 1000 simulations using shiny app "BOIN" available at <http://www.trialdesign.org>. The operating characteristics show that the design selects the true MTD, if any, with high probability and allocates more patients to the dose levels with the DLT rate closest to the target of 0.3.

Table 3. Operating characteristics of the Boin design (Dose 0 is the starting dose)

	Dose Level -2	Dose Level -1	Dose Level 0 (starting dose)	Dose Level 1	Number of Patients	% Early Stopping
Scenario 1						
True DLT Rate	0.47	0.55	0.64	0.75		
Selection %	44.2	27.6	8.2	0.1		19.9
% Pts Treated	24.4	36	37.7	1.9	11.8	
Scenario 2						
True DLT Rate	0.11	0.3	0.47	0.67		
Selection %	9.1	52.5	34.3	3.2		0.9
% Pts Treated	5.8	33.8	52	8.4	11.8	
Scenario 3						
True DLT Rate	0.02	0.13	0.3	0.47		
Selection %	0.3	19.3	54.5	25.6		0.3
% Pts Treated	0.4	15.7	58.1	25.9	11.7	
Scenario 4						
True DLT Rate	0.05	0.1	0.15	0.3		
Selection %	0	2.4	26.6	71		0
% Pts Treated	0	3.1	43.8	53.2	11.9	

Phase II:

In phase II portion of the study, patients will be treated at the RP2D level chosen during phase 1b for each arm separately. A maximum of 30 patients will be treated in each arm. For AML patients, the primary efficacy endpoint is overall response, defined as CR, CRh, CRi, PR or marrow clearance of blasts within 3 cycles of treatment. For MDS patients, the primary efficacy endpoint is overall response, defined as CR, PR, HI (Hematologic Improvement), or mCR (marrow clearance of blasts) within 3 cycles of treatment. In addition, we will continue to monitor the DLTs that occurred during the first 3 cycles of treatment.

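### The Phase 2 toxicity boundaries are set only at full cohorts of 6; the plan does not say what happens if one is reached mid-cohort, when further enrolment can no longer change the decision

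*Combined protocol and SAP*

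**What the plan says.** Section 8.0, Phase II, monitors response and toxicity together in each arm with a BOP2 design and a maximum of 30 patients. Toxicity is the DLT: "we will continue to monitor the DLTs that occurred during the first 3 cycles of treatment". An arm stops enrolling, and the regimen is called unacceptable, when the posterior probability that the DLT rate is at most 0.2 falls below λ(n/N)^(α/3). The plan explains the factor 3 as a change made "to obtain stricter interim stopping boundaries to enhance safety".

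The rule is then turned into counts: "The above decision rule leads to the following optimal stopping boundaries, in cohort size of 6". The limits appear under "Table 4: Optimized stopping boundaries for AML Arm" and "Table 6: Optimized stopping boundaries for MDS Arm":

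| Patients treated | 6 | 12 | 18 | 24 | 30 |
|---|---|---|---|---|---|
| AML: stop if DLTs at least | 2 | 3 | 4 | 6 | 7 |
| MDS: stop if DLTs at least | 2 | 3 | 4 | 5 | 7 |

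The text after each table describes the criteria as non-binding. Section 8.5 adds a summary report after every 10 evaluable patients have completed 3 cycles. That is not a within-cohort rule, and it does not line up with looks every 6. No section says what to do when a limit is reached between looks.

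**The concern.** A look every 6 patients is needed for futility, because a response count can still rise while the cohort fills. Toxicity is different. Once the number of patients with a DLT equals the next look's limit, that look can have only one result. Patients enrolled after that point are exposed to a regimen that the plan's own rule will call unacceptable, and they contribute nothing to the decision. The sponsor tightened the toxicity cutoff for safety, but that change affects the size of the limits and not when they act. What is at stake is a small number of patients per arm, mostly when the regimen really is too toxic.

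**Working it through.** **1. The limits.** Both Dirichlet priors give toxicity a Beta(0.2, 0.8) marginal (AML 0.04 + 0.16 = 0.20; MDS 0.03 + 0.17 = 0.20). With x DLTs in n patients the posterior is Beta(0.2 + x, 0.8 + n − x). The cutoffs use λ = 0.5, α = 0.51 (AML) and λ = 0.52, α = 0.15 (MDS).

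- AML, n = 6: cutoff 0.5 × (6/30)^0.17 = 0.380. Pr(p_tox ≤ 0.2) is 0.658 with 1 DLT and 0.279 with 2, so the limit is 2.
- At n = 24, 5 DLTs give 0.499. The AML cutoff is 0.481 (continue, limit 6). The MDS cutoff is 0.514 (stop, limit 5).

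All 20 response and toxicity limits in the two tables reproduce.

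**2. The stated operating characteristics, and the effect of stopping at the crossing.** The check is an exact patient-by-patient multinomial recursion under the scenarios of Tables 5 and 7. It was run first with stops only at the five looks, and then with enrolment stopped at the patient whose DLT brings the count to the next look's limit. Futility stays at full cohorts. Cells show early stopping % / claim acceptable % / average N. Savings come from unrounded values.

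| Arm, scenario (p_eff, p_tox) | Stated | Looks only | Stop at crossing | N saved |
|---|---|---|---|---|
| AML 1 (0.20, 0.20) | 85.03 / 10.44 / 12.8 | 85.19 / 10.25 / 12.71 | 85.95 / 10.25 / 11.82 | 0.89 |
| AML 2 (0.40, 0.10) | 25.31 / 73.93 / 24.8 | 25.26 / 74.05 / 24.80 | 25.43 / 74.05 / 24.53 | 0.27 |
| AML 3 (0.40, 0.25) | 80.66 / 15.88 / 13.4 | 80.88 / 15.87 / 13.34 | 83.08 / 15.87 / 11.95 | 1.39 |
| AML 4 (0.15, 0.30) | 98.07 / 0.77 / 8.5 | 98.09 / 0.78 / 8.46 | 98.48 / 0.78 / 7.02 | 1.45 |
| MDS 1 (0.15, 0.20) | 88.41 / 9.77 / 11.5 | 89.05 / 9.25 / 11.43 | 89.27 / 9.25 / 10.57 | 0.86 |
| MDS 2 (0.30, 0.10) | 34.21 / 65.36 / 23.0 | 34.60 / 64.96 / 22.91 | 34.65 / 64.96 / 22.63 | 0.28 |
| MDS 3 (0.30, 0.25) | 86.01 / 12.85 / 12.5 | 86.29 / 12.50 / 12.52 | 86.95 / 12.50 / 11.14 | 1.39 |
| MDS 4 (0.10, 0.30) | 98.89 / 0.69 / 7.8 | 99.07 / 0.57 / 7.73 | 99.16 / 0.57 / 6.37 | 1.36 |

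The stated figures reproduce with looks at 6, 12, 18, 24 and 30 only. The largest gap in a type I error is MDS 9.77 against 9.25, about 1.8 Monte Carlo standard errors for 10,000 runs. The probability of claiming acceptable is the same with and without the earlier stop in all eight scenarios. In AML scenario 4 the expected number of patients with a DLT falls from 8.46 × 0.30 = 2.54 to 7.02 × 0.30 = 2.1.

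**3. Why the saving is bounded.** Successive limits rise by at least 1, and an arm that continues is at least 1 below the limit just passed. Every cohort therefore needs at least 2 new DLTs to cross. The earliest crossing is at its second patient, which leaves at most 4 places.

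**4. Reporting lag.** Let the lag be the number of further patients who start before the crossing is confirmed. In the first cohort the expected saving at lag L is the sum of P(at least 2 DLTs in m patients) over m = 2 to 5 − L. At p_tox = 0.30 these probabilities are 0.090, 0.216, 0.348 and 0.472 for m = 2, 3, 4 and 5:

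- lag 0: 0.090 + 0.216 + 0.348 + 0.472 = 1.13 patients
- lag 2: 0.090 + 0.216 = 0.31
- lag 3: 0.09
- lag 4: 0

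Over the whole arm, by simulation at p_tox 0.25 to 0.30, the average saving is 0.34 to 0.39 at lag 2, about 0.1 at lag 3, and exactly 0 at lag 4 or more. At p_tox 0.10 it is 0.06 at lag 2. DLTs are monitored over 3 cycles of 4 to 6 weeks (Section 4.3), that is 12 to 18 weeks, and a hematologic DLT needs cytopenia lasting at least 6 weeks (Section 6.2.1). No accrual rate is given, so the lag cannot be derived from the documents.

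**The case against.** Four points deserve weight.

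- *The plan may already allow this.* The criteria are non-binding, and the general rule is an inequality in the interim sample size n. Two DLTs in the first two patients give a posterior probability of 0.021, below cutoffs of 0.316 (AML) and 0.454 (MDS). This stands in part: an early stop is permitted. But the tables and simulations use looks every 6. Applying the inequality after every patient would be a different design: an AML arm would stop on a DLT in its first patient, and at 5 DLTs among 19 to 23 patients, where the scheduled limit at 24 is 6.
- *A DLT count can be revised.* Section 6.2.1 makes a DLT depend on the investigator finding no other clear cause, and Section 7.5.1.5 lets causality be reassessed. This stands. The argument needs confirmed DLTs.
- *The saving may be nil.* With a long DLT window and quick accrual, four or more patients could start before the crossing is known. This stands. The rule then saves nothing, but it also costs nothing in decisions.
- *Cohort monitoring is the stated basis of the design.* This stands as well. The figures in Tables 5 and 7 are sound for the rule they describe.

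A reader might infer that the plan orders four more patients to be treated after two DLTs in the first two. No section says so; the plan is silent.

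**Conclusion.** The gap is real but small. The toxicity limits are specified and simulated only at full cohorts, and nothing covers a crossing between looks. If the limits are followed and DLTs are confirmed, stopping at the crossing gives the same go/no-go result in every trial. The average saving per arm has an upper limit of about 1.4 patients at p_tox 0.25 to 0.30 and 0.3 at p_tox 0.10, with at most 4 in any one trial. It shrinks to nothing once four patients can start before a crossing is known.

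Two stronger readings are tempting. One is that a stop is certain once the count is reached; the non-binding status and the possible re-attribution of a DLT prevent that. The other is that the operating characteristics are wrong; they reproduce. This is an optional, inexpensive improvement that serves the safety aim the plan already states.

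**What to change.** Add to Section 8.0, Phase II, for both arms:

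> Confirmed DLTs are counted as they occur. If the number of patients with a confirmed DLT reaches the toxicity boundary of the next scheduled look before that cohort is full, the boundary is treated as met and enrolment to that arm stops then, with the same (non-binding) status as the scheduled looks.

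Keep the futility looks at complete cohorts, and do not re-apply the posterior formula after each patient. In Tables 5 and 7, update both average sample size and early stopping %, because a crossing in the last cohort can now end an arm before 30 (AML scenario 3: 80.9% to 83.1% at lag 0). State the reporting lag assumed. The claim-acceptable column does not change.

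The cost is a running count of confirmed DLTs and a slightly smaller denominator for the descriptive response and safety estimates. Type I error and power are unaffected.
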